10.1.3.6. Numerical serology results

Numerical serology results will be derived Based on each assay cut-off (=LLOQ), using the following derivation rules

IS.ISORRES	Derived value
"NEG", "-", or "(-)"	cut-off/2
"POS", "+", or "(+)"	cut-off
"< value" and value is ≤ assay cut-off	cut-off/2
"< value" and value is > assay cut-off	value
"> value" and value is < assay cut-off	cut-off/2
"> value" and value is ≥ assay cut-off	value
"value" and value is < cut-off	cut-off/2
"value" and value is ≥ cut-off	value
All other cases	missing

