**5.7.5. Immunological correlates of protection**

The following cut-offs are accepted as immunological correlates of protection:

- Specific antibodies against diphtheria toxoid (anti-diphtheria) and tetanus toxoid (anti-tetanus) will be measured by Enzyme-linked immunosorbent assay (ELISA), for which the threshold of 0.1 International Units per ml (IU/ml) provides a conservative estimate of the percentage of subjects deemed to be protected [[Camargo, 1984](#); [Melville-Smith, 1983](#)].
- Antibodies against the hepatitis B surface antigen (anti-HBs) will be measured using ChemiLuminescence ImmunoAssay (CLIA). The cut-off of the test is set at 6.2 mIU/ml. An antibody concentration ≥ 10 mIU/ml defines seroprotection [[CDC, 1991](#)].
- Antibodies against poliovirus types 1, 2 and 3 will be determined by a virus micro-neutralisation test adapted from the World Health Organization Guidelines for WHO/EPI Collaborative Studies on Poliomyelitis [[WHO, 1993](#)]. Titres will be

expressed in terms of the reciprocal of the dilution resulting in 50% inhibition. Samples with a titre greater than or equal to 1:8 will be considered as seropositive and protective.

- Data from subjects given unconjugated Hib vaccine suggest that, in the absence of induction of immunological memory, a concentration of 0.15 µg/mL is indicative of short-term protection, with 1 µg/mL considered indicative of long-term protection [Käyhty, 1983; Anderson, 1984].
- No serological correlate of protection against pertussis has been established [Plotkin, 2010]. Antibodies against the pertussis components pertussis toxoid (PT), filamentous haemagglutinin (FHA) and pertactin (PRN) will be measured by ELISA. The seropositivity cut-off for all three pertussis antibodies in ELISA is 5 EL.U/ml. Subjects with antibody concentration below the cut-off will be considered seronegative.

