**Table 17 Reference values (booster phase)**

**(Amended 12 December 2016)**

Reference Study	Observed seroprotection rates		Booster response for Pertussis antigens			Observed Seroprotection rates				
	D	T	PT	FHA	PRN	PRP	HBs	Anti-IPV1	Anti-IPV2	Anti-IPV3
DTPa-HBV-IPV-095	100.0% [97.7, 100]	100.0% [97.7,100]	93.3% [88.1, 96.8]	86.0% [79.6, 91.0]	98.1% [94.4, 99.6]	99.4% [96.5,100]	100% [97.7,100]	100% [97.5,100]	100% [97.5,100]	100% [97.5,100]
DTPa-HBV-IPV 083 [Full term infants (≥37 weeks)]	100.0% [94.7, 100]	98.5% [92.1, 100]	97% [89.5,99.6]	98.5% [92, 100]	98.5% [92,100]	100% [94.7,100]	98.5% [92.1,100]	100% [94.6,100]	100% [94.6,100]	100% [94.3,100]
DTPa-HBV-IPV 083 [Pre-term infants (<37 weeks)]	100.0% [95.7, 100]	100.0% [95.7, 100]	100% [95.7,100]	97.6% [91.7, 99.7]	100% [95.7,100]	100% [95.7,100]	91.6% [83.4,96.5]	100% [95.5,100]	100% [95.5,100]	100% [95.1,100]
DTPa-HBV-IPV 081	100.0% [96.8, 100]	100.0% [96.8, 100]	98.2% [93.8,99.8]	98.2% [93.8,99.8]	99.1% [95.2,100]	100% [96.8,100]	99.1% [95.2,100]	100% [96.6,100]	100% [96.6,100]	100% [96.3,100]
217744/054	100.0% [97.9,100.0]	100.0% [97.9,100.0]	100.0% [97.8,100.0]	100.0% [97.8,100.0]	100.0% [97.9,100.0]	100.0% [97.9,100.0]	98.9 (95.9,99.9)	100.0% [97.6,100.0]	100.0% [97.5,100.0]	100.0% [97.5,100.0]

DTPa-HBV-IPV 095 (Germany): Group primed with *Infanrix hexa* according to 2,4,6 schedule and received a booster dose of *Infanrix hexa* between 11-23 months.

DTPa-HBV-IPV 083 (Spain): Group primed with *Infanrix hexa* according to 2,4,6 schedule and received a booster dose of *Infanrix hexa* between 18-20 months of age.

DTPa-HBV-IPV 081 (Germany): Group primed with *Infanrix hexa* according to 3,4,5 schedule and received a booster dose of *Infanrix hexa* between 12-23 months of age

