### 10.5. Derived and transformed data

The cut-off value is defined by the laboratory before the analysis and is described in Section 5.7.3.

- A seronegative subject is a subject whose antibody concentration/titre is below the assay cut-off.
- A seropositive subject is a subject whose antibody concentration/titre is greater than or equal to the assay cut-off defined in Table 7.
- A seroprotected subject is a subject whose antibody concentration/titre is greater than or equal to the level defining clinical protection. The following seroprotection thresholds are applicable:
  - Anti-diphtheria antibody concentrations  $\geq 0.1$  IU/ml.
  - Anti-tetanus antibody concentrations  $\geq 0.1$  IU/ml.
  - Anti-HBs antibody concentrations  $\geq 10$  mIU/mL.
  - Anti-poliovirus types 1, 2 and 3 antibody titres  $\geq 8$ .
  - Anti-PRP antibody concentrations  $\geq 0.15$   $\mu$ g/ml.
- Other cut-offs to be considered:
  - Anti-PRP antibody concentrations  $\geq 1.0$   $\mu$ g/ml.
  - Anti-diphtheria antibody concentrations  $\geq 1.0$  IU/ml.
  - Anti-tetanus antibody concentrations  $\geq 1.0$  IU/ml.
  - Anti-HBs antibody concentrations  $\geq 100$  mIU/mL.
- For the pneumococcal antigens, the threshold used for statistical analysis will depend on the final selected assay.
- Booster response to the PT, FHA and PRN antigens, is defined as:

- initially seronegative subjects (pre-booster antibody concentration below cut-off: < 5 ELISA EL.U/mL) with an increase of at least four times the cut-off one month after vaccination (post-booster antibody concentration  $\geq$  20 EL.U/mL), and
- initially seropositive subjects with pre-booster antibody concentration  $\geq$  5 EL.U./mL and < 20 EL.U/mL with an increase of at least four times the pre-booster antibody concentration one month after vaccination, and,
- For initially seropositive subjects with pre-booster antibody concentration  $\geq$  20 EL.U/mL with an increase of at least two times the pre-booster antibody concentration, one month after vaccination.

*Note:* Due to ongoing re-validation of pertussis assays and potential change in the assay unit, the definition of booster response may be subject to change.

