3.3. Primary endpoint

- Immunogenicity with respect to components of *Infanrix hexa*.
 - Anti-diphtheria, anti-tetanus, anti-HBs, anti-poliovirus type 1, anti-poliovirus type 2, anti-poliovirus type 3 and anti-polyribosyl-ribitol phosphate (anti-PRP) seroprotection status, one month after the booster dose.
 - Booster response to PT, FHA and PRN antigens, one month after the booster dose.

Refer to section 5.3.2 for the definition of the booster response

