5.3. Immunogenicity

5.3.1. Analysis of immunogenicity planned in the protocol

The primary analysis will be based on the ATP cohort for analysis of immunogenicity. If in any vaccine group, the percentage of enrolled subjects excluded from this ATP cohort is more than 5%, a second analysis based on the TVC will be performed to complement the ATP analysis. All analyses will be descriptive.

For each group, at each time point that a blood sample result is available:

- Seropositivity rates against PT, FHA and PRN antigens and pneumococcal antigens (1, 3, 4, 5, 6A, 6B, 7F, 9V, 14, 18C, 19A, 19F, 23F) with exact 95% CI [Clopper, 1934] will be calculated.
- Seroprotection rates against diphtheria toxoid, tetanus toxoid, HBs, PRP antigen and poliovirus types 1, 2, 3 antigens (with exact 95% CI [Clopper, 1934]) will be calculated.
- Percentage of subjects with anti-pneumococcal serotypes (1, 3, 4, 5, 6A, 6B, 7F, 9V, 14, 18C, 19A, 19F, 23F) antibody concentrations, depending on the GSK laboratory or WHO reference laboratory assay cut-offs, will be calculated along with its exact 95% CI [Clopper, 1934].
- Percentage of subjects with anti-D and anti-T antibody concentrations ≥ 1.0 IU/ml will be calculated along with its exact 95% CI [Clopper, 1934].
- Percentage of subjects with anti-PRP antibody concentrations ≥ 1.0 $\mu\text{g/ml}$ and anti-HBs antibody concentrations ≥ 100 mIU/mL will be calculated along with its exact 95% CI [Clopper, 1934].
- GMC/GMT with 95% CI will be tabulated for antibodies against each antigen.
- The booster response rates to PT, FHA and PRN (with exact 95% CI) one month after the booster dose will be calculated.

The above summaries will be provided by country or primary vaccination schedule for countries involving more than 50 subjects.

- The distribution of antibody concentrations/titres for each antigen will be displayed using reverse cumulative distribution curves (RCCs).
- The distribution of antibody concentrations or titres of each antigen will be tabulated.

Handling of missing data:

- For a given subject and a given immunogenicity measurement, missing or non-evaluable measurements will not be replaced. Therefore, an analysis will exclude subjects with missing or non-evaluable measurements.

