8. CHANGES FROM PLANNED ANALYSES

- During the course of the study, the assays used to measure the anti-D, anti-T, anti-PT, anti-FHA and anti-PRN IgG concentrations were re-developed and re-validated and both assay units and assay cut-offs were adapted. The new ELISA's for PT, FHA and PRN were calibrated against the WHO International Standard (NIBSC 06/140). This allowed the expression of concentrations measured with the new ELISA's in international units per milliliter (IU/mL) instead of the formerly used ELISA units per milliliter (ELU/mL). The newly validated DTPa ELISA's used in the study have a lower assay cut-off as compared to the one described in the protocol. The current assay cut-off is 0.057 IU/mL for anti-D, 0.043 IU/mL for anti-T, 2.693 IU/mL for anti-PT, 2.046 IU/mL for anti-FHA and 2.187 IU/mL for anti-PRN. An agreement between the old and new ELISAs was shown with regards to the two thresholds of clinical relevance for the DI/TE response (0.1 IU/mL and 1.0 IU/mL) and therefore the clinical endpoints and anti-D and anti-T are unchanged. In the absence of a correlate of protection for the B. pertussis antigens, the pertussis endpoints were redefined based on the assay cut-off (see section 5.7.5 of protocol).

CONFIDENTIAL

201334 [DTPA (BOOSTRIX) -049 BST: 048]
Statistical Analysis Plan Final

- Note: Due to re-validation of all assays, the cut-offs presented in Table 7 of the protocol of few antigens have changed. Below table has an updated threshold.

Antigen	Threshold for positivity
• Anti-PT	• 2.693 IU/mL
• Anti-FHA	• 2.046 IU/mL
• Anti-PRN	• 2.187 IU/mL
• Anti-D	• 0.057 IU/mL
• Anti-T	• 0.043 IU/mL
• Anti-polio	• 8 dilution
• Anti-PRP	• 0.066 µg/mL
• Anti-HBs	• 6.2 mIU/mL
• Anti-pneumococcal serotypes (1)	• 0.080 µg/mL
• Anti-pneumococcal serotypes (3)	• 0.075 µg/mL
• Anti-pneumococcal serotypes (4)	• 0.061 µg/mL
• Anti-pneumococcal serotypes (5)	• 0.198 µg/mL
• Anti-pneumococcal serotypes (6A)	• 0.111 µg/mL
• Anti-pneumococcal serotypes (6B)	• 0.102 µg/mL
• Anti-pneumococcal serotypes (7F)	• 0.063 µg/mL
• Anti-pneumococcal serotypes (9V)	• 0.066 µg/mL
• Anti-pneumococcal serotypes (14)	• 0.160 µg/mL
• Anti-pneumococcal serotypes (18C)	• 0.111 µg/mL
• Anti-pneumococcal serotypes (19A)	• 0.199 µg/mL
• Anti-pneumococcal serotypes (19F)	• 0.163 µg/mL
• Anti-pneumococcal serotypes (23F)	• 0.073 µg/mL

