10. ANNEXES

10.1. Business rules for standard data derivations and statistical methods

This section contains GSK Vaccines' standard rules for data display and derivation for clinical and epidemiological studies. These rules will be applied along with those detailed in section 9 (additional study-specific rules).

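### The SAP's rule for results reported as 'less than' a value assigns the excluded upper bound, so any such result at a protection threshold would be counted as seroprotected

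*SAP*

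**What the plan says.** SAP 10.1.3.6 is a table of derivation rules applied to each assay against its own cut-off, which it equates with the LLOQ. A 'less than' result with a bound at or below the cut-off becomes half the cut-off. For "< value' and value is > assay cut-off", the derived value is the value itself. The table sits in SAP 10.1, described as the sponsor's "standard rules for data display and derivation for clinical and epidemiological studies", and that section says the rules will be applied in this study.

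Protocol 10.5 makes the thresholds inclusive: "A seroprotected subject is a subject whose antibody concentration/titre is greater than or equal to the level defining clinical protection". It lists 0.1 IU/mL for anti-D and anti-T, 10 mIU/mL for anti-HBs, a titre of 8 for poliovirus and 0.15 µg/mL for anti-PRP. Protocol 5.7.5 repeats the hepatitis B limit: "An antibody concentration ≥ 10 mIU/ml defines seroprotection".

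SAP 8 lowers several cut-offs after assay re-validation: "The current assay cut-off is 0.057 IU/mL for anti-D, 0.043 IU/mL for anti-T". Its table adds 0.066 µg/mL for anti-PRP and leaves anti-HBs at 6.2 mIU/mL. The primary endpoint in SAP 3.3 includes "seroprotection status, one month after the booster dose" for these antigens. On missing data, SAP 5.3.1 says: "For a given subject and a given immunogenicity measurement, missing or non-evaluable measurements will not be replaced".

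**The concern.** A result reported as '<10' says that the concentration is strictly below 10. Replacing it by 10 and then asking whether it is at least 10 turns a known failure into a success. This can happen only where the assay cut-off lies below the clinical threshold, and under SAP 8 that holds for anti-HBs, anti-D, anti-T and anti-PRP.

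Seroprotection one month after the booster is a primary endpoint, and pre-booster seroprotection is a secondary one. For both, the error would run one way: this row can raise a seroprotection rate but never lower it. The estimated rates and their exact intervals are what the study delivers, so the rule behind them should be right even if it is seldom used.

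**Working it through.** **Inputs.** Derivation rows: SAP 10.1.3.6. Cut-offs: SAP 8, with Protocol Table 7 for comparison. Seroprotection thresholds: Protocol 10.5. Further limits: Protocol 10.5 and SAP 5.3.2. Evaluable numbers per group: Protocol Table 16 (272, 238, 204).

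**Rule as coded.** For '< v' with cut-off c, the derived value is c/2 if v ≤ c, and v otherwise. The subject is protected if the derived value is at least the threshold T.

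**Applied with v = T and the SAP 8 cut-offs:**

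| Result | Cut-off | Derived value | Threshold | Scored | True status |
|---|---|---|---|---|---|
| anti-HBs '<10' | 6.2 | 10 | 10 | protected | not protected |
| anti-D '<0.1' | 0.057 | 0.1 | 0.1 | protected | not protected |
| anti-T '<0.1' | 0.043 | 0.1 | 0.1 | protected | not protected |
| anti-PRP '<0.15' | 0.066 | 0.15 | 0.15 | protected | not protected |
| poliovirus '<8' | 8 | 4 | 8 | not protected | not protected |

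**With the Protocol Table 7 cut-offs** (0.1 for anti-D and anti-T, 0.15 for anti-PRP), '<0.1' becomes 0.05 and '<0.15' becomes 0.075, both correctly not protected. Only anti-HBs is then affected. For the other three antigens the gap arises from the lowered cut-offs in SAP 8.

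**Other bounds.** A bound between cut-off and threshold is classed correctly; for example, anti-HBs '<7.65' becomes 7.65, below 10. A bound above the threshold, such as anti-HBs '<20', is scored protected although the true status is unknown.

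**Other limits.** The same row would count '<1.0 IU/mL' (anti-D, anti-T), '<1.0 µg/mL' (anti-PRP), '<100 mIU/mL' (anti-HBs) and '<0.35 µg/mL' (pneumococcal serotypes) as reaching those limits. Every pneumococcal cut-off in SAP 8 is below 0.35; the highest is 0.199.

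**Size.** The Clopper-Pearson calculation was first checked against the 100% rows of Protocol Table 16: lower limits of 98.7 (272/272), 98.5 (238/238) and 98.2 (204/204), all as printed. One misclassified infant moves a rate by:

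- 1/272 = 0.37 points
- 1/204 = 0.49 points

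As an illustration, assume one such result in a group that is otherwise fully protected. At n=272 the rule reports 100% [98.7, 100], where the correct figure is 271/272 = 99.6% [98.0, 100.0]. At n=204 it reports 100% [98.2, 100], where the correct figure is 203/204 = 99.5% [97.3, 100.0]. The documents give no number of such results, so one is an assumption and zero is possible.

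**The case against.** The strongest reply is that the row may never be reached. SAP 10.1.3.6 itself equates cut-off with LLOQ, so a result above the cut-off would normally be reported as a number. For anti-HBs, Protocol 10.5 says that results between 6.2 and 7.65 mIU/mL are quantified as 6.2, which is correctly below 10, and names 7.65 as the LLOQ, so values from 7.65 to 10 should be quantifiable. For anti-D and anti-T, SAP 8 reports agreement between old and new assays at 0.1 IU/mL, which suggests that this level is within the measurable range. All of this stands. It makes such results unlikely, but it does not correct the row that exists to handle them.

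A second reply is that no passage says seroprotection is classified on the derived value. Protocol 10.5 speaks of the subject's concentration, and a concentration known to be below 10 does not meet that definition. The half-cut-off substitution is tied to GMT/GMC calculation. This also stands as far as it goes: the link is inferred. The inference is reasonable, because SAP 10.1.3.6 covers numerical serology results generally, SAP 10.1.3.7 treats GMTs and GMCs separately, and the SAP defines no other numerical result.

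The generic origin of the table is not a defence, since SAP 10.1 applies it to this study. Nor does the missing-data rule in SAP 5.3.1 help: the row gives these results a number, so they are not treated as non-evaluable.

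In the other direction, a reader might take the unprotected fractions implied by the reference rates in Protocol Table 17 as the size of the problem, most tempting of all for the pre-term anti-HBs rate of 91.6%. The documents do not support that. It would require every unprotected infant to have a censored result with a bound at or above the threshold, whereas a numeric value below the threshold or a result below the cut-off is classed correctly. It would also apply a pre-term rate to a whole group.

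**Conclusion.** The row is wrong as written, for any result censored at a protection threshold above the assay cut-off, and no other passage corrects it. The conclusion rests on two conditions: that seroprotection is classified on the derived value, which is inferred, and that such results occur, which the documents do not show. The supportable size is possibly zero, and about 0.4 points (n=272) or 0.5 points (n=204) per result.

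A reader might infer that the primary seroprotection rates are inflated. The documents support only that they could be, and only upwards through this row. SAP 6 makes all analyses descriptive, so no test, error rate or success criterion is affected. Severity: minor.

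**What to change.** Amend the 'less than' row of SAP 10.1.3.6 for bounds above the cut-off:

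- For any threshold T, a '< value' result is never counted as at or above T when value ≤ T.
- When value > T, the result is non-evaluable for T and is not replaced, in line with SAP 5.3.1.
- State separately which value such a result takes in the GMC/GMT, because the threshold rule does not settle that.
- Report the number of such results, and how many are non-evaluable, by group and antigen. Only if any are non-evaluable, add a sensitivity analysis counting them as not protected.

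The rule should cover the further limits (1.0 IU/mL, 1.0 µg/mL, 100 mIU/mL, 0.35 µg/mL) as well as the seroprotection thresholds.

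The cost is a short change to the SAP wording and one derivation. A few results may become non-evaluable and some rates slightly lower. Leaving non-evaluable results out of the denominator can itself raise a rate, which is why the count and the conditional sensitivity analysis are needed. If no such result occurs, nothing in the reported analysis changes.

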10.1.3.7. Geometric mean titres (GMTs) and concentrations (GMCs)

Geometric Mean Titre (GMT) or Concentration (GMC) calculations are performed by taking the inverse logarithm of the mean of the log titre or concentration transformations. Antibody titres or concentrations below the cut-off of the assay will be given an arbitrary value of half the cut-off of the assay for the purpose of GMT/GMC calculation. The cut-off value is defined by the laboratory before the analysis and is described in the protocol.

10.1.3.8. Onset day

The onset day for an event (e.g. AE, medication, vaccination) is the number of days between the last study vaccination and the start date of the event. This is 1 for an event occurring on the same day as a vaccination (and reported as starting after vaccination).

10.1.3.9. Duration of events

The duration of an event with a start and end date will be the number of days between the start and end dates plus one day, i.e. an event that starts on 03MAR2018 and ends on 12MAR2018 has a duration of 10 days.

The duration of solicited events will be calculated as the sum of the individual days with the symptom reported at grade 1 or higher.

10.1.3.10. Counting rules for combining solicited and unsolicited adverse events

For output combining solicited and unsolicited adverse events, all serious adverse events will be considered general events since the administration site flag is not included in the expedited adverse event CRF pages.

Multiple events with the same preferred term which start on the same day are counted as only one occurrence.

